### **Informed Consent**

Written informed consent will be obtained prior to data collection or randomization. The risk of harm or discomfort is expected to be negligible, as the intraoperative questionnaire is short and not expected to extend the length of surgery more than 15 minutes. In addition, the clear mask has been approved for use in the operating room by the Food and Drug Administration and is not expected to increase the risk of infection compared to the standard covered mask. The rights and welfare of study participants will be protected by using measures to maintain the confidentiality of study information. Study results will be presented or published in lieu of providing individual subjects additional information regarding the study.

### **Confidentiality and Privacy**

Confidentiality will be protected by collecting only information needed to assess study outcomes, minimizing the collection of any information that could directly identify subjects, and maintaining all study information in a secure manner. To help ensure subject privacy and confidentiality, only a unique study identifier will appear on the data collection form. Any collected patient identifying information corresponding to the unique study identifier will be maintained on a linkage file, stored separately from the data. The linkage file will be kept secure, with access limited to designated study personnel. Following data collection, subject identifying information will be destroyed in three years (consistent with data validation and study design), producing an anonymous analytical data set. Data access will be limited to study staff. Data and records will be kept locked and secured, and any computer data will be password protected. No reference to any individual participant will appear in reports, presentations, or publications that may arise from the study.

### **Data and Safety Monitoring**

The principal investigator will be responsible for the overall monitoring of the data and safety of study participants. The principal investigator will be assisted by other members of the study staff.

### **Reporting of Unanticipated Problems, Adverse Events or Deviations**

Any unanticipated problems, serious and unexpected adverse events, deviations, or protocol changes will be promptly reported by the principal investigator or designated member of the research team to the IRB and sponsor or appropriate government agency if appropriate.

## **Appendix 1. Hearing Screening**

**Patient ID:** \_\_\_\_\_

Date: \_\_\_\_\_

**Rater:** \_\_\_\_\_

## **Hearing Handicap Inventory in the Elderly – Screening Questionnaire**

*Instructions: Answer Yes, No, or Sometimes for each question. Do not skip a question if you avoid a situation because of a hearing problem. If you use a hearing aid, please answer according to the way you hear with the aid.*

1. Does a hearing problem cause you to feel embarrassed when you meet new people?
2. Does a hearing problem cause you to feel frustrated when talking to members of your family?
3. Do you have difficulty hearing when someone speaks in a whisper?
4. Do you feel handicapped by a hearing problem?
5. Does a hearing problem cause you difficulty when visiting friends, relatives, or neighbors?
6. Does a hearing problem cause you to attend religious services less often than you would like?
7. Does a hearing problem cause you to have arguments with family members?
8. Does a hearing problem cause you difficulty when listening to TV or radio?
9. Do you feel that any difficulty with your hearing limits or hampers your personal or social life?
10. Does a hearing problem cause you difficulty when in a restaurant with relatives or friends?

Yes (4) No (0) Sometimes (2)

$\mathbf{Y}_t = (\mathbf{1})^\top \mathbf{N}_t (\mathbf{0})^\top \mathbf{S}_t + \mathbf{e}_t$  (2)

$Y_1 = 6$ ,  $N_1 = 8$ ,  $S_1 = 1$ ,  $i_1 = 2$

### Total Score:

Interpretation of Total Score: 0-8 = no handicap; 10-24 = mild to moderate handicap; 26-40 = severe handicap.

Adapted from: Ventry I, Weinstein B. Identification of elderly people with hearing problems. *ASHA*. 1983; 25:37-42.

## Appendix 2. Data collection form

Patient ID: \_\_\_\_\_

Neurologist: \_\_\_\_\_

Group Assignment:  A – Clear

B – Covered

**Mask type used:** Clear / Covered

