## **Interventions and Interactions**

Patients who both elect to undergo DBS surgery and agree to participate in this study will have a record created in the study database. All patients scheduled for a DBS phase I surgery will be contacted via telephone in the days prior to their scheduled surgery to discuss the possibility of study participation. This will be done to give the patient time to consider study participation in order to avoid delays the morning of surgery. The morning of surgery the patient will be approached in pre-operative holding room to discuss participation in the study and if amenable sign consent for participation. This discussion will inform the patient that minor changes are being made in an attempt to improve the patient experience, but limited information regarding what steps exactly will be provided so as to reduce potential bias that might result from the patient knowing we are studying a new mask type. If the patient agrees to participation, a consent form will be signed and as a baseline will undergo the Hearing Handicap Inventory for the Elderly (HHIE-S) questionnaire before the operation (Appendix 1). The patient's record in the electronic study database will then be created and randomized to one of two groups. Group A will experience the neurologist wearing a clear mask, and group B will experience the neurologist wearing a standard covered mask. The patient and all other intra-operative personnel will wear a covered surgical mask.

Following standard surgical protocol, the DBS surgery will proceed with the patient awake. First, a stereotactic frame is securely attached to the patient's head and the patient is positioned appropriately. Local anesthetic is used for the neurosurgeon to obtain access through the scalp and skull. A microelectrode is then stereotactically placed using headframe coordinates. The neurosurgeon sets up the motor apparatus to allow the neurologist to advance the microelectrode to the appropriate deep brain target, operating the motor from a non-sterile station arranged next to the patient. The microelectrode will stimulate and record neuronal activity, during which time the neurologist will ask the patient questions to assess for changes in symptoms. These questions typically are of the following nature:

- Do you notice any tingling or pulling of the mouth or face?
- Do you see any flashes of light in your vision?
- Do you feel any tingling or heaviness of an arm or leg?

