- Do you notice any metallic or strange taste?
- Can you draw a spiral on this piece of paper?
- Can you hold your arm out in front of you and keep it still?

During a routine DBS surgery, the neurologist is positioned in view of the patient while operating the electrode motor and asking the above questions. Microelectrode stimulation and recording will conclude

when the appropriate target has been reached; that is, when simulation achieves both symptom improvement without new neurologic symptoms. At that point, the microelectrode is withdrawn and the macroelectrode is placed. The macroelectrode is stimulated in the determined position to again confirm symptom improvement without new neurologic symptom or deficit, and when confirmed the neurosurgeon will secure the macroelectrode in place. At this point, the neurologist's testing portion is complete, and the neurologist exits the operating room while the neurosurgeon completes the implantation.

For patients who agree to study participation, the neurologist will wear the mask type assigned by the randomization group for the duration of involvement in the surgery. At the conclusion of the neurologist's interaction with the patient, the patient will be asked a series of questions (presented in Appendix 2, Data collection form) to evaluate the communication experience. This step will be performed by another member of the study team (not the participating neurologist) who will read from the questionnaire and record the patient's responses using the Likert scale (defined in Appendix 2). During questioning, the neurologist will step out of the operating room to reduce potential bias from the patients answering subjective questions in front of the neurologist.

At the conclusion of the questionnaire, the patient will undergo a short debriefing regarding the aims of the study, specifically the revelation that the purpose of the study is to evaluate the use of a clear surgical mask on the patient's experience, as assessed by the questionnaire.

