At the conclusion of the neurologist's assessment, as is typical, the patient will be placed under sedation for the completion of the DBS implantation. In the event a patient is having bilateral DBS implantation in one operation, only the first DBS implantation will be included in the study. For these patients, the procedure will be carried out as stated above, but following the first DBS implantation the neurologist will continue to interact with the patient for the second DBS implantation. The second implantation will not be included in the study data collection.

A retrospective chart review will be conducted for the 30 day post-operative period to evaluate for surgery-related infection. Evaluating for rates of infection between mask groups will help to ensure there is no harm associated with use of a non-covered mask during the operation. The patients will not need to be contacted or otherwise actively participate in the study during this period; information will be obtained via medical record review only. For such a chart review, a waiver of consent will be completed in the IRB application. Such a waiver is necessary in order to answer the study question regarding mask safety and surgery-related infection, as it would be difficult to retrospectively re-consent every patient already enrolled in this nearly-complete study.

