## **Outcomes and Statistical Plan**

Data will be gathered based on the attached Data Collection Form (Appendix 2). Answers to the questionnaire will be deidentified.

Power calculations will be performed considering the primary endpoint of a dichotomous response to question #1 of the CG-CAHPS. Thirty subjects per group will be needed to achieve 80% power to detect a difference of 26% or more between proportions (hypothesized standard of care mask positive response rate of 73% versus clear mask positive response rate of 99%) with alpha of 5% using conservative two-sided Fisher's Exact Test. Therefore the enrollment goal will be 60 subjects total.

Secondary outcomes will include differences in response to the remaining quantitative questions of the CG-CAHPS and free text responses to the final question. As the quantitative question responses are on a Likert scale, responses 1-3 will be considered negative and 4 will be considered positive thereby converting the outcome to binary according to the top box method. Fisher's Exact Test will be used to investigate a difference between the standard of care mask and the clear mask for all dichotomous outcomes. P-values < 0.05 will be considered statistically significant. A content analysis will be performed on the free responses to investigate distinct themes.

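### Nothing in the plan keeps the arm from the person who records the spoken primary outcome, and that person's form has fields for the arm above question 1

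*Combined protocol and SAP*

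**What the plan says.** The Outcomes and Statistical Plan section makes the dichotomised answer to CG-CAHPS question 1 the primary endpoint. Under its top-box rule, "responses 1-3 will be considered negative and 4 will be considered positive".

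Interventions and Interactions says how the answer is obtained. After the neurologist's part ends, the patient is questioned by "another member of the study team (not the participating neurologist) who will read from the questionnaire" and who records the replies. The questions are those on the Appendix 2 data collection form. The header of that form has a field for "Group Assignment" (A clear, B covered) and one for "Mask type used" (clear or covered). Question 1 comes below them, and the two items about the mask come at the end.

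The stated protections against bias are these:
- Patients are not told that the mask is the topic until the questionnaire is finished (Interventions and Interactions; Subject Recruitment Methods).
- The neurologist does not ask the questions.
- During questioning "the neurologist will step out of the operating room to reduce potential bias" from patients answering in front of that person.

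On what can be seen in the room, the same section says: "The patient and all other intra-operative personnel will wear a covered surgical mask". In Group A the neurologist's mask is therefore the only clear one.

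**The concern.** Each stated protection concerns the patient's knowledge or freedom to answer. None concerns the interviewer. The documents leave two routes open by which that person could know the arm before asking question 1:
- **The form.** The arm fields share a sheet with the outcome, and the plan does not say who marks them or when.
- **The room.** Anyone present during testing in Group A could see the clear mask, and the plan does not say where the interviewer is at that time.

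The study identifier described under Confidentiality and Privacy protects the patient's identity; it does not conceal the arm.

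What is at stake is one cut in a subjective spoken rating. The patient supplies the number, so an arm-aware interviewer could influence it only through tone, prompting, or how an unclear reply is written down. With 30 patients per arm, one reply moved across the cut changes the observed difference by 1/30 = 3.3 points.

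**Working it through.** **Inputs from the Outcomes and Statistical Plan:** 30 per arm; top-box rates of 73% (standard mask) and 99% (clear mask); two-sided Fisher's exact test; significance at p < 0.05. **Assumed, because the documents give no figure:** the size and direction of any shift in recorded answers.

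**Method.** For recorded top-box probabilities p₁ (covered) and p₂ (clear), the probability of rejection is the sum, over all i and j from 0 to 30, of Bin(i; 30, p₁) × Bin(j; 30, p₂) wherever Fisher's p for the table [i, 30 − i; j, 30 − j] is below 0.05.

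**The plan's own figure first.** With p₁ = 0.73 and p₂ = 0.99 the exact power is 0.781, against the stated 80%. It is 0.805 at 31 per arm. The stated figure reproduces to within 2 points, and the sample size does not depend on the present point.

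**No true effect, 73% in both arms:**

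| Assumed shift in recorded answers | p₁ (covered) | p₂ (clear) | Rejection |
|---|---|---|---|
| None | 0.730 | 0.730 | 2.6% |
| Clear arm up by one answer (3.3 points) | 0.730 | 0.763 | 3.2% |
| Clear arm up 5 points (1.5 answers) | 0.730 | 0.780 | 4.0% |
| Clear arm up about 6.4 points (1.9 answers) | 0.730 | 0.794 | 5.0% |
| Clear arm up 10 points (3 answers) | 0.730 | 0.830 | 9.1% |
| One answer up in clear, one down in covered | 0.697 | 0.763 | 5.2% |
| 5 points up in clear, 5 down in covered | 0.680 | 0.780 | 8.7% |

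**Clear arm only.** The expected number of non-top answers in that arm is 30 × 0.27 = 8.1. Reaching 5% means moving 1.9 of them, or 1.9/8.1, about 24%. The crossing point lies between 6.4 and 7.3 points for base rates from 60% to 85%. If only half the clear-arm interviews were arm-aware, the shift within them would have to be twice as large, 12.9 points, which is 12.9/27 = 48% of their non-top answers.

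**Both arms.** With equal shifts in opposite directions, 5% is reached at about 3.2 points per arm: 0.032 × 30, or about one answer in each.

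**Effect on the estimate.** One moved answer adds 3.3 points, or 3.3/26 = 13% of the planned difference. One in each arm adds 2/30 = 6.7 points, about 26% of it.

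**Where answers could move under the planned effect.** At 99% the clear arm has only 30 × 0.01 = 0.3 expected non-top answers, so upward recording there has almost no room. The covered arm has 30 × 0.73 = 21.9 expected top answers, so downward recording does have room.

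**Reach of a change made now.** Take the clear-arm-only shift that gives 5.0%, and assume it is removed for the last 3 of the 30 clear-arm patients. Rejection falls to 4.5%. If it is removed for the last 6, rejection falls to about 4%.

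**The case against.** The strongest reply is that this reports a missing statement, not an error. The patient is the rater. The questions are fixed and read from a form by someone other than the neurologist, who is out of the room, and the mask items come last. An unmarked header prints both options and reveals nothing. The patient sees the mask in any case, so blinding the interviewer cannot take the mask out of the measurement. One moved clear-arm answer leaves the test below 5%.

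Most of this stands, and it sets the importance of the point. A reader might infer from the header that the interviewer knows the arm, or that the primary result is biased. The documents do not support either inference: they do not say who marks the fields, when, or where the interviewer is during testing.

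Two parts do not stand. First, the existing safeguards reduce the interviewer's room for influence but do not address knowledge of the arm. Second, the comfort drawn from the 6.4-point figure holds only if shifts are upward and confined to the clear arm. An arm-aware interviewer could also mark covered-arm answers down, and then about one answer in each arm is enough.

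The objection that a remedy comes late is also fair. The plan describes patients as "already enrolled in this nearly-complete study".

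**Conclusion.** The point holds as an unguarded possibility. The plan puts arm and primary outcome on one sheet, gives that sheet to the person recording a spoken rating, and nowhere keeps the arm from that person.

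The size depends on shifts that are assumed throughout. With a true 73% in both arms and 30 per arm, rejection stays at or below 5% for clear-arm-only shifts up to about 6.4 points. It reaches 5% at about 3.2 points per arm if the arms move in opposite directions. A claim that the type I error is in fact inflated would need evidence of such shifts, and the documents contain none.

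This is a cheap improvement to consider. It does not call the design or the sample size into question.

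**What to change.** For remaining patients:
- Move both arm fields to a separate sheet or database screen, linked by study ID and completed by someone other than the interviewer. Keep both, because together they check that the assigned mask was worn.
- Where existing staffing allows, have the interviewer enter only after the neurologist has left. Splitting the form does not blind someone who has seen the mask.
- Add one Y/N field: did the interviewer know the arm before question 1?

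The interviewer still needs the neurologist's name to read the item on trust.

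For patients already enrolled, state in the report that the interviewer was not required to be blind to arm.

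The cost is one linked record, one field and one sentence. No new system is needed, because the patient's "record in the electronic study database will then be created and randomized to one of two groups". The downsides are that few patients would benefit this late, that two collection methods would exist side by side, and that later entry depends on staffing the plan does not describe. The reported limitation is the main gain.

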### CG-CAHPS Questions

- \* Did this provider explain things in a way that was easy to understand?
- \* Did this provider listen carefully to you?
- \* Did this provider seem to know the important information about your medical history?
- \* Did this provider show respect for what you had to say?
- \* Did this provider spend enough time with you?

1 = Not at all  
4 = Completely

1 2 3 4  
1 2 3 4  
1 2 3 4  
1 2 3 4  
1 2 3 4

### Additional Questions

- \* Did this provider demonstrate empathy?
- \* How comfortable do you feel trusting Dr. (Neurologist)'s decisions?
- \* Did you understand what you were being asked to do?
- \* How satisfied are you with the procedure thus far overall?

1 2 3 4  
1 2 3 4  
1 2 3 4  
1 2 3 4

1 = Strongly disliked  
4 = Strongly liked

† What was your impression of the Neurologist's mask?

1 2 3 4

§ What comments do you have about the Neurologist's mask(s)? \_\_\_\_\_

\* 4-point Likert scale (1=not at all, 4=完全); †4-Likert scale (1=strongly disliked, 4=strongly liked); § Free response; Abbreviations: CH-CAHPS, Clinician and Group Consumer Assessment of Healthcare Providers and Systems
